For the Phase I study, the sample size of 15 participants per group will allow detection of an increase in adverse events of 13% with 88% statistical power using a 2-sided alpha of 0.10. The sample size will allow assessment of a difference of 35% in seroconversion between groups after a complete vaccination series or after a single vaccination at a similar statistical power. The sample size will also allow assessment of a difference in geometric mean titers by ELISA, determined by analysis of variance, between dose levels (low dose versus high dose) of 35% with 86% statistical power at an alpha of 0.10. These results will be used to guide selection of vaccination regimen for Phase IIa.

For the Phase IIa study, the sample size of 300 participants, randomized 2:1 vaccine to placebo will allow detection of a difference in adverse events of 18% with 82% statistical power at alpha of 0.05. The sample size will allow assessment of a difference in seroconversion between groups of at least 10% with greater than 95% statistical power at alpha of 0.05. For a sample size of 126 participants, randomized 2:1 vaccine to placebo will yield 80% probability to detect a difference in the rate of adverse events of 28% or greater. A sample size of N=126 will allow detection of a difference in seroconversion of 14% with 80% statistical power. Safety and immunogenicity will be determined at planned Interim Analysis and after all vaccinations are completed.

Safety assessments:

Participants will be monitored at each study visit for adverse events. Laboratory safety assessments will be performed as indicated in the schedule of events to determine whether there are any changes in hematologic parameters, electrolytes, or renal function relative to pre-vaccination assessment. Subjects administered GLS-5310 will be followed for a year from their first vaccination with GLS-5310 regardless of initial study arm randomization. In the Phase IIa study, subjects, will be followed for 48 weeks from first vaccination, however, subjects assigned to placebo and who chose to be vaccinated with GLS-5310, will be followed for a year from first vaccination with GLS-5310 or a total of 60 weeks.

Immunogenicity analysis:

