17. Immunosuppression including immunodeficiency disease or family history
18. Positive of serum test at screening of Hepatitis B surface antigen, Hepatitis A IgM, HIV, or Hepatitis C. Persons who are Hepatitis C seropositive, and for whom an HCV RNA test is negative, are allowed into the study.
19. Baseline screening lab(s) with Clinically Significant abnormality (Grade 2 or higher)
20. Serious adverse reaction to a drug containing Investigational Product (GLS-5310) or other ingredients of the same categories or to a vaccine or antibiotic, nonsteroidal anti-inflammatory disease control, etc. or an allergic history
21. History of hypersensitivity to vaccination such as Guillain-Barre syndrome
22. History of PCR-confirmed infection with SARS-CoV-2 or positive SARS-CoV-2 antibody or PCR test at screening
23. Subjects who have been contact with COVID-19 infections in the past prior to administration, have been classified as COVID-19 confirmed patients, medical patients or patients with symptoms or have been identified with SARS and MERS infection history in the past
24. Acute over 37.5°C fever, cough, difficulty breathing, chills, muscle aches, headache, sore throat, loss of smell, or loss of taste within 72 hours prior to administration
25. Healthcare workers participating in the medical examination of patients infected with COVID-19 or high-risk individuals who are likely to be occupationally exposed to SARS-CoV-2
26. Not willing to allow storage and future use of samples for SARS-CoV-2 related research
27. Prisoner or subjects who are compulsorily detained for treatment of a psychiatric illness
28. Any illness or condition that, in the opinion of the investigator, may affect the safety of the subject or the evaluation of a study endpoint

29. Receipt of a vaccine to prevent COVID-19 infection

Safety evaluation analysis method: Adverse events occurring after vaccination are summarized according to frequency, and presented according to SOC and PT along with the number and ratio of subjects with adverse events. The continuous response variable at each time point and the change from baseline are summarized as mean, median, minimum and maximum values. Categorical response variables are summarized as a percentage for each time point.

Data for the Phase IIa study will be unblinded after database lock for analysis. Since subjects who were randomized to placebo will have the opportunity to be given the vaccine, safety assessments can be divided into 3 groups:

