7.1.5 Visit 4: Post-vaccination follow-up, unblinding

Study procedures to be completed include:

- Review and record concomitant medications
- Perform targeted physical exam (relevant to participant system-specific complaints)
- Perform and record vital signs
- Review and record adverse events
- Review and record injection site reactions
- Collect blood for hematology and chemistry
- Collect blood for immunology testing (serum and PBMCs)
- Inform participant of their treatment assignment
 - For those who received placebo, ask whether they would like to start vaccination series with GLS-5310(Refer to Section 7.2)

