11.1 Data Sets to be Analyzed

- The intention to treat population (ITT) includes all participants who sign informed consent.
- The modified intention to treat population (mITT) includes all participants who sign informed consent and who has received at least one administration of study drug. The mITT population will be the primary analysis population for outcomes.
- The safety set (SS) includes all participants who have received at least one dose of study medication. The SS will be the primary group for safety evaluations and outcome. Analysis of immune responses will be performed only for available samples.

Per-protocol (PP) analysis set includes all participants who complete the trial and who receive all vaccinations and have no significant protocol violations. Participants in this sample will be grouped to treatment arms they actually received. This set will be used as a sensitivity analysis to summarize the primary and secondary efficacy outcomes. For secondary and exploratory assessments of antibody and T cell immune responses, denominators will include only those participants who are SARS-CoV-2 seronegative at baseline. Unevaluable samples will not be considered as part of the denominator at relevant time points. For study participants who are seropositive at baseline, separate assessment of antibody and T cell responses will be performed.

The Phase IIa portion of the study will be unblinded at the post-vaccination visit (visit 4) and all persons who were randomized to the placebo arm offered vaccination with GLS-5310. Safety assessments will be determined based on the actual treatment received. Persons randomized to the placebo group who elect vaccination with GLS-5310 will then be considered to cross-over to the vaccination group as of Week 12. Persons randomized to the placebo group, and who decline vaccination will remain as part of the placebo group, regardless of whether such persons receive any other COVID-19 vaccine. Any study participant who receives an approved COVID-19 vaccine will remain as part of the group assignment as above.

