4.1 Interim Analysis

Interim analyses were performed in stages.

- **Stage 1:** An assessment of AE's was performed after study Visit 1 for Group 1a.
- **Stage 2:** When all Phase I subjects (Groups 1a, 1b and 1c) had completed Visit 4, an interim analysis was performed to evaluate safety and antibody response.
In order for the study to move into Phase IIa study, the seroconversion rate for the binding antibody responses must be >70%. In addition, the incidence of Serious Adverse Events (Grade 3 or higher) related to the investigational product should be no more than 1 case.
- **Stage 3:** An interim analysis of Phase IIa study was performed after all patients complete their Visit 4. The purpose of this interim analysis was to provide options to placebo vaccinated subjects and to assess the safety of the vaccine after the second dose. For the interim analysis of Phase IIa, database locking was implemented before unblinding.

The study is unblinded at the post-vaccination visit (study Visit 4) at which time subjects are informed of their treatment assignment. Subjects who were assigned to the placebo group are offered to be vaccinated with GLS-5310. Subjects assigned to the placebo group who choose to be vaccinated with GLS-5310 are followed for a year from 1st GLS-5310 vaccination; subjects assigned to the placebo group but who decline vaccination with GLS-

CONFIDENTIAL

5310 are followed for a year from study entry as per the original study protocol.

5. Determination of Sample Size

This is an exploratory and descriptive Phase I/Ila clinical trial to evaluate the safety and immunogenicity of GLS-5310 for the purpose of preventing COVID-19, and dose not test statistical hypotheses, so the sample size is set within the limit of satisfying the research purpose. In the Phase I clinical trial, 45 subjects who meet the inclusion and exclusion criteria are registered to secure 15 subjects based on the allocation of each vaccination group. In the Phase Ila clinical trial, it is planned to secure 120 subjects based on randomization.

Randomization is performed 1:1 in 1b and 1c groups of Phase I clinical trial according to the planned random number, and 1:2 in placebo and vaccination groups in Phase Ila clinical trial to determine the difference between placebo and vaccination groups.

6. Analysis Sets

Safety and tolerability analyses will be performed on Safety Set.

✓ **Intention to treat (ITT)**

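### Protocol 11.1 dates the placebo crossover at Week 12 rather than at the first GLS-5310 dose, and SAP 4.1 describes an unblinding sequence under which that date would be too early

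*Protocol*

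**What the plan says.** Protocol 11.1 says that a placebo participant who chooses GLS-5310 "will then be considered to cross-over to the vaccination group as of Week 12". The same paragraph says "Safety assessments will be determined based on the actual treatment received".

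Most of the protocol puts disclosure at Week 12. Section 7.1.5 lists, among the Visit 4 procedures, "Inform participant of their treatment assignment". Sections 3 and 8.3.3 agree, and the title of Table S4 has the GLS-5310 series chosen at that visit. The synopsis (safety assessments) says these participants "will be followed for a year from first vaccination with GLS-5310 or a total of 60 weeks".

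Other text puts database lock first. The synopsis (safety evaluation analysis method) says "Data for the Phase IIa study will be unblinded after database lock for analysis", and Protocol 11.8 is similar. SAP 4.1, Stage 3, reports: "An interim analysis of Phase IIa study was performed after all patients complete their Visit 4". It continues: "The purpose of this interim analysis was to provide options to placebo vaccinated subjects", and then: "For the interim analysis of Phase IIa, database locking was implemented before unblinding". The closing paragraph of SAP 4.1 nevertheless says that participants are told their assignment at Visit 4, as does SAP section 3.

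**The concern.** With staggered entry, lock after everyone's Visit 4 and disclosure at each participant's own Visit 4 cannot both precede the offer of GLS-5310. If lock came first, all but the latest enrollees would have waited past Week 12 for their first GLS-5310 dose, and the latest would have waited for the lock itself. Protocol 11.1 would still place them in a vaccine group from Week 12, so an adverse event that arose when only placebo had been given would be reported under vaccine.

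Safety is a primary objective, and the crossover safety tables depend on which side of the dividing date an event falls. Week 12 is the only dividing date that either document states.

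**Working it through.** **Inputs from the documents.** Visit 4 is at Week 12, ±3 days (Table S2). Follow-up after the first GLS-5310 dose is 48 weeks (Table S4). The stated total is 60 weeks (synopsis). There are 40 placebo participants (Table S1). Recruitment is about 5 months for the whole trial and study length about 20 months (synopsis, section 3).

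**Assumptions.** Phase IIa entry is uniform over R = 1 to 5 months, lock takes L = 0 to 8 weeks, and 1 month = 4.35 weeks. The documents give neither R for Phase IIa alone nor L.

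1. *The plan's own figure.* 12 + 48 = 60 weeks. It reproduces only if there is no delay between Week 12 and the first GLS-5310 dose.

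2. *Disclosure and dosing at own Visit 4.* The gap is about 0, apart from the ±3-day visit window.

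3. *Lock first.* A participant who enters at time u waits (R − u) + L beyond their own Week 12. The mean gap is R/2 + L, the maximum is R + L, and mean total follow-up is 60 + R/2 + L.

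| R (months) | L (weeks) | Mean gap (weeks) | Maximum gap (weeks) | Mean total follow-up (weeks) |
|---|---|---|---|---|
| 1 | 0 | 2.2 | 4.3 | 62.2 |
| 1 | 4 | 6.2 | 8.3 | 66.2 |
| 2 | 4 | 8.3 | 12.7 | 68.3 |
| 5 | 0 | 10.9 | 21.7 | 70.9 |
| 5 | 8 | 18.9 | 29.7 | 78.9 |

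4. *Fit to the stated study length.* Phase IIa cannot open before the arm 1a Week 1 review and then the Week 16 Visit 4 of arm 1c: 1 + 16 = 17 weeks at least. The whole trial then needs 17 + 60 + R + L = 77 + R + L weeks, against 20 × 4.35 = 87. So R + L can be about 10 weeks. The last row needs 77 + 29.7 = 106.7 weeks and does not fit. At R + L = 10 the mean gap is 10 − R/2, which for R = 1 month (4.35 weeks) is 7.8 weeks. A mean gap of about 2 to 8 weeks is therefore compatible with the stated length.

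5. *Effect on counts.* Suppose all 40 cross over and a fraction p has at least one adverse event in any 4 weeks without vaccine (p is assumed). The expected number with an event in a gap of g weeks is 40 × (1 − (1 − p)^(g/4)). For p = 5%, 10% and 20% this gives 1.0, 2.1 and 4.2 participants at g = 2, and 2.7, 5.3 and 10.4 at g = 5.4.

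6. *Does any other rule settle it?* A crossed-over participant received both treatments, so grouping by treatment received does not say where an event in the gap belongs. The SAP has a separate Re-vac. group (10.1) but no rule for splitting one participant's events. It counts treatment-emergent events from the initial vaccination (10.2), takes baseline at or before the start of investigational product (8.4), and imputes a wholly missing event start date to the first administration (8.2, Table 1). For these participants each of those dates is already fixed by the first placebo injection, and no restart is stated.

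**The case against.** The strongest reply is that disclosure at Visit 4 is the dominant reading. It appears throughout the protocol and twice in the SAP, and the lock sentences may refer only to unblinding for analysis. On that reading the gap is close to zero and Week 12 does no harm. This has force, and a reader who concluded from Stage 3 that the SAP unblinds only after lock would go too far. But Stage 3 links the interim analysis to the options offered to placebo participants, so the lock-first sequence cannot be ruled out either.

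A reader might also infer that placebo time is counted as exposure in the randomised vaccine arm. The documents do not support that. The synopsis forbids pooling the two vaccine groups, Protocol 11.8 analyses the crossover participants separately, and SAP 10.1 keeps a Re-vac. group and measures exposure in vaccinations and milligrams. SAP 10.2.1 reports participants, incidence and events, so no person-time result is at risk. The main safety summary covers events within 28 days of administration at the interim analysis (Protocol 11.3.1). What remains is that 11.1 names the vaccination group without distinguishing the two.

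A further inference is that disclosure at each participant's own Visit 4 would void the blinded comparison for early enrollees. That is not supported. Both doses and follow-up up to Visit 4 are blinded, 7.1.5 lists disclosure after the adverse event review and blood draws, and 8.3.3 keeps assay staff blinded until the assay is complete.

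**Conclusion.** Wrong as written: an internal inconsistency that affects the crossover safety tables, not sample size, power or the randomised comparison up to Visit 4. Protocol 11.1 is harmless if GLS-5310 began at each participant's own Visit 4. Under the lock-first sequence it would assign events that preceded any GLS-5310 dose to vaccine, and the 60-week total would be too short.

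The size depends on R, L and uptake, none of which is given for Phase IIa. The mean gap is about 0 on one reading and about 2 to 8 weeks on the other; values near 19 weeks are hard to fit into about 20 months. The 17-week minimum allows no time for Phase I enrolment, analysis or board review, and the 20 months is itself approximate, so the upper end is a rough guide. The documents do not establish which sequence was followed, so misassignment is a consequence of the rule under one sequence, not a demonstrated fact.

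**What to change.** In Protocol 11.1, replace Week 12 as the crossover date with the date of the first GLS-5310 dose, state that events before that dose stay under placebo, and name the separate Re-vac. group as the destination.

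In the SAP, start the Re-vac. group's baseline, treatment-emergent definition and adverse event date imputation at that dose, and state how one participant's events are split between Placebo and Re-vac.

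Reconcile the synopsis, Protocol 7.1.5, 8.3.3 and 11.8, and SAP 4.1 to one described sequence of disclosure, lock and unblinding for analysis, and check the 60-week figure against it. Because SAP 4.1 reports the interim lock as already done, the record should be clarified rather than removed, and a data freeze before disclosure cannot be added in retrospect.

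The cost is wording in both documents, plus one derived date taken from the dosing record. It should be done before the final tables are produced.

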11.2 Demographic and Other Baseline Characteristics

Demographic and baseline data, vital signs, medical history, concomitant illnesses, and current medications/treatments, including surgeries will be summarized by means of descriptive statistics: continuous variables as mean, median, standard deviation, and categorical variables as frequencies and percentages.

11.3 Safety Analysis

All safety and tolerability summaries will be performed on the SS.

11.3.1 Adverse events

Treatment emergent AEs will be summarized by frequencies and will be presented by system organ class and preferred term with the number and percentage of participants affected. Frequencies will be presented with respect to maximum severity and to strongest relationship to Study Treatment. Multiple occurrences of the same AE will be counted only once following a worst-case approach with respect to severity and relationship to Study Treatment.

Treatment emergent AEs will be summarized by estimates of proportions with exact 95% binomial CIs. The differences in proportion between the groups will also be calculated with 95% CIs. These frequencies will be summarized overall, by system organ class and by preferred term, for the number and percentage of participants affected. Additional frequencies will be presented with respect to maximum severity and to strongest relationship to Study Treatment. All serious AEs and administration site events will also be summarized as above.

The main summary of safety data will be based on events occurring within 28 days of administration of Study Treatment at the time of interim analysis; long term safety will be assessed through to 48 weeks following the final vaccination for each group.

VAS scores will be summarized with mean, median, minimum, and maximum values.

11.3.2 Laboratory Data

Continuous response variables per time point and changes from baseline will be summarized with mean, median, minimum, and maximum values. Categorical response variables will be summarized per time point with percentages.

11.4 Immune Response Analysis

The study is not designed or powered to determine efficacy of the vaccine. However, immune response to the vaccine may be assessed by responder analysis of the immunogenicity data.

Immunogenicity results will be classified as responder/non-responder and will be analyzed as the frequency of responses for each assay for each treatment arm at each time point at which an assessment is performed. Estimates of proportions and exact 95% binomial CIs and 95% CIs for the differences between the groups will be calculated.

Immunogenicity analysis will be performed in the mITT and PP groups with evaluable immune response data.

11.5 Interim Analysis

An assessment of AE's will be performed after study visit 1 for Group 1a. For the Phase I study, an interim analysis will be performed after study visit 4. In order to enter Phase IIa, the seroconversion rate for the binding antibody reaction between test groups is evaluated on the basis of >70%. In addition, the incidence of serious adverse events (Grade 3 or higher) related to the investigational drug is evaluated as 1 or less. For the Phase IIa study, an interim analysis will be performed after study visit 4.

11.6 Sample Size and Randomization

This clinical trial is a phase 1/2a clinical trial to evaluate the safety and immunogenicity of GLS-5310 for the purpose of preventing COVID-19 set the required number of subjects.

For the phase 1 study, 45 subjects who meet the inclusion and exclusion criteria will be enrolled in order to secure 15 subjects to be vaccinated for investigational drugs for each vaccination group. For the phase 2a study, it was planned to secure 120 subjects based on randomization.

Randomization was performed 1:1 in groups 1b and 1c of the phase 1 study according to the pre-planned randomization generation number, and 2a, 2b in the phase 2a study to determine the difference between placebo and vaccine randomization is performed 1:2 in groups.

11.7 Missing Values

In the event that dates and/or times are missing for medications, medications will be assumed to be concomitant. In the event dates or times are missing for AEs, AEs will assume to be treatment emergent. Missing outcomes values, such as missed lab draws or invalid blood sample, missed vital signs, or missed or uninterpretable serum concentrations and PBMCs will be left as missing and not imputed. For the immunology analyses, statistical assessment will be based on available results.

In the event that a participant is enrolled in the trial but declines to be vaccinated then the site will enroll a replacement.

11.8 Unblinding

For safety analysis the study will be unblinded after database lock for analysis. Since subjects who were randomized to placebo will have the opportunity to be given the vaccine, safety assessments can be divided into 3 groups:

- 1) Randomized to vaccine
- 2) Randomized to placebo
- 3) Subset of Placebo subjects who received vaccine after unblinding

In addition, among the subjects assigned to the GLS-5310 vaccination group and the placebo group, the GLS-5310vaccinated group and the revaccinated group are analyzed separately.

12. DATA COLLECTION, MONITORING AND AE REPORTING

12.1 Confidentiality

Information about study participants will be kept confidential to the best of the study site's ability.

If a study participant cancels consent to the collection or use of personal health information (PHI), the sponsor may continue to use the information collected prior to the cancellation of the informed consent. For subjects who revoke consent to collection or use of PHI, consent should be obtained

for collection of critical conditions (i.e., survival of study participant), at least before completion of their planned clinical trial period.

